## 8.7 Monitoring Period

Continuous monitoring from either Capnostream™ 20p or Nellcor Monitoring Systems will be performed on all patients for a minimum of 24 hours. The monitoring period will last up to patient's full mobilization or up to a maximum of 72 hours, if the patient is still bed-ridden after two days post-surgery.

The monitoring period will start for patients once they arrive on the ward. For patients who are determined to be at high risk due to opioid therapy and not due to other pre-existing factors, monitoring of capnography and pulse oximeter data will start only after opioid therapy has been initiated.

Monitoring may be discontinued if the patient is discharged from the hospital ward.

During Phase I the alarm feature of the monitoring devices will be silenced and the screen information blinded. A regular check during the monitoring period should be completed to ensure the etCO2 filter line and SpO2 sensors are appropriately fitted on the patient.

During Phase II the medical staff will be instructed to respond to alarm feature of the monitoring devices and their screen will be open. A guideline will be created to instruct the nurses in responding to alarms and changes in the monitored parameters. An alarm will be considered a false positive by the observer if the SpO2 sensor or the etCO2 filter line is off the patient or misplaced. Alarms will be considered true positive if the SpO2 sensor and etCO2 filter line placement is correct: observations on patient activity and subsequent interventions will be recorded in the eCRF to identify clinically significant or insignificant alarmed events. As an example, patient activities such as talking, eating or gripping a book with the SpO2 sensor compressed will be marked as true positive with details of the activity recorded to identify the alarmed event as potentially clinically insignificant if no medical intervention was taken. The Monitoring eCRF will be completed to document:

- Care pathway (location/transfer within hospital)
- Alarm threshold applied to the monitor (to be collected during the Monitoring Phase II only for each measured parameter, PR, RR, SpO2 and EtO2).
- Systolic blood pressure and level of consciousness using the AVPU scale to allow the retrospective NEWS analysis
- Monitoring duration
- Vital signs
- Supplemental oxygen use
- Medications
- Product information

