**Table 5. Anticipated Respiratory Adverse Events**

Partial airway obstruction that required an NMBA antagonist
Respiratory Insufficiency that would require Non-invasive positive pressure ventilation, ambu bag mask assisted ventilation
Respiratory failure that would require Invasive mechanical ventilation
Upper airway obstruction requiring airway support measures (oral or nasal) such as intubation or Laryngeal Mask Airway
Respiratory insufficiency/failure that would require a transfer to the ICU
Cardiopulmonary arrest
Death due to respiratory/pulmonary related complications

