**Table 3 - Protocol Deviation by Reason - FAS**

**Table 4 - Protocol Deviation by Visit - FAS**

**Listing 1 - Other deviations – FAS**

### 7.1.3. Analysis Sets

The following patient sets will be used for the analysis:

- The Full Analysis Set (FAS) includes all patients actively enrolled in the study, who signed Informed Consent Form (ICF), fulfilled the inclusion/exclusion criteria and monitored by CS20p or PM1000N. The FAS will be used to describe both baseline characteristics and safety outcomes of the study population;
- The Per Protocol Set (PPS) includes all patients in the FAS, without major protocol deviations, who have at least 24 hours of monitoring *effective time*. The PPS will be used to describe baseline characteristics of the study population and to evaluate the primary and secondary endpoints. Patient with poor quality of device data, defined as having less than 90% of time continuously monitored, will be included or excluded from the PPS, as appropriate.

The following table shows how each population set will be used for analyses:

Population set	Baseline assessment	Primary and Secondary Endpoint #1	Secondary Endpoints #2, #3, #4 and #5	Safety AE Death
FAS	✓		✓	✓
PPS	✓	✓	✓	

For those patients who have less than 24 hours or poor quality of device data monitoring or who withdrew, the analyses will include all data up to the point of their last data collection only for FAS population.

An additional set could be created during the analysis phase, in case necessary to investigate on a particular subgroup of patients.

 Effective time is the cumulative time with valid recorded data. This aimed to filter out periods of time where the patient was not connected to the Capnography cannula or pulse-ox sensor, but recording was on-going (the patient was not monitored during this time).

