## 7.9. Evaluation of Objectives

### 7.9.1. Primary Endpoint

The Primary Endpoint of the Study is to quantify the incidence of RC markers in high risk postsurgical patients, using a system comprised of two continuous monitoring devices, connected to a remote monitoring platform. The proportion and rate of “At least one RC marker” event will be calculated and reported.

The “At least one RC marker” event is defined as the occurrence of at least one of the following RC markers:

1.  $\text{SpO}_2 \leq 90\%$  for  $\geq 3$  minutes (or  $\text{SpO}_2 \leq 90\%$  for  $< 3$  min with an action taken);
2.  $\text{RR} \leq 8$  or  $\geq 22$  bpm for  $\geq 3$  minutes (or  $\text{RR} \leq 8$  or  $\geq 22$  bpm for  $< 3$  min with an action taken);
3.  $\text{EtCO}_2 \leq 15$  or  $\geq 60$  mmHg for  $\geq 3$  minutes (or  $\text{EtCO}_2 \leq 15$  or  $\geq 60$  mmHg for  $< 3$  min with an action taken);
4. Apnea episode lasting  $> 30$  seconds.

For patients monitored by PM1000N, only RC markers #1 and #2 will be considered.

RC determination will be assessed by a physician belonging to the “other” site (cross assessment by the sites). This assessment will be made by the analysis of both device and clinical data for each patient. For each patient all potential RC episodes will be derived using the Detection Tool (see Section 10.1) and will be submitted to the other site’s physician in order to adjudicate the potential RC episodes starting from episodes most likely to be RC. The adjudication will stop at the first RC occurring per patient.

The Events’ rates will be computed as (total number of “At least one RC marker” event)/(total number of time-person in PPS) and will be reported separately for each arm and phase of the study. Events’ rates will be displayed together with their 95% confidence interval (95%CI).

If the number of episode per patient result unbalanced, adjusted rates will be reported using the GEE model, together with their 95% confidence interval (95%CI).

If appropriate, also the events’ rates for each RC marker will be reported separately, for each arm and phase of the study.

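### The SAP's primary analysis set requires 24 hours of effective monitoring whatever the reason for stopping, so set membership can depend on the outcome; Protocol 12.3 names the FAS instead

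*SAP*

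**What the plan says.** SAP 7.1.3 defines the PPS as the set that "includes all patients in the FAS, without major protocol deviations, who have at least 24 hours of monitoring", measured as effective time, meaning cumulative time with valid recorded data. It adds: "The PPS will be used to describe baseline characteristics of the study population and to evaluate the primary and secondary endpoints". The table in that section ticks only the PPS for the primary endpoint and secondary endpoint #1; the FAS is ticked for baseline, secondary endpoints #2 to #5 and safety. For patients with under 24 hours, poor device data or withdrawal, "the analyses will include all data up to the point of their last data collection only for FAS population".

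SAP 7.9.1 follows suit: the denominator of the primary rate is the "total number of time-person in PPS". On when the endpoint is reached, it says "The adjudication will stop at the first RC occurring per patient".

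Protocol 12.3 says the opposite about the set: the primary final analysis uses the FAS, less patients who fail the eligibility criteria.

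On how monitoring can end early, Protocol 8.7 states "Monitoring may be discontinued if the patient is discharged from the hospital ward". Protocol 8.12 lists an adverse event among the reasons for withdrawal and does not replace withdrawn patients other than screen failures. Protocol Appendix A, Table 5, anticipates "Respiratory insufficiency/failure that would require a transfer to the ICU", along with invasive ventilation, cardiopulmonary arrest and death.

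**The concern.** One marker lasting 3 minutes, or in the Capnostream arm one apnea of more than 30 seconds, meets the endpoint. No minimum observation time is needed. Take a patient with a qualifying desaturation at hour 5 whose monitoring ends at hour 6 on transfer to the ICU. This patient has met the endpoint, but has 6 hours of effective time and so is absent from the PPS. Whether a patient belongs to the primary set can thus depend on what happened to that patient.

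Two results are exposed: the primary incidence, reported by arm and phase, and secondary endpoint #1, the phase comparison of it. Phase II alarms are meant to change early deterioration, so the loss could differ between phases and enter the comparison as if it were an effect of monitoring.

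**Working it through.** **The plan's own figure.** SAP section 6 gives 182 evaluable patients for a 95% interval of ±5 points at 10%, achieved with probability at least 0.80. With exact (Clopper-Pearson) intervals the smallest such n is 179, and at 182 the probability is 0.855. Inflation gives 182 × 1.15 = 209.3, or 182/0.85 = 214.1, against about 210 stated. The SAP figure reproduces. (Protocol 12.1 has 260 in the same place; 260 × 1.15 = 299 does not give 210.) The SAP therefore plans for about 210 − 182 = 28 patients outside the evaluable set.

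**Loss of deteriorating patients, all 210.** Inputs: 10% incidence (SAP 6), so 21 endpoint patients; respiratory failure 0.2–3.4% (Protocol 3.1). Assumptions: half occur before 24 hours, all of these patients had met the endpoint, and all stop monitoring. With k patients lost, the estimate is (21 − k)/(210 − k).
- 0.2%: k = 210 × 0.002 × 0.5 = 0.21; 20.79/209.79 = 9.9%.
- 3.4%: k = 210 × 0.034 × 0.5 = 3.57; 17.43/206.43 = 8.4%.

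The SAP calls 10% a minimum. Protocol 3.1 cites up to 37% with prolonged saturation below 90%. At 37% there are 77.7 endpoint patients, and k = 3.57 gives 74.13/206.43 = 35.9%.

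**Loss within a reporting cell.** Phase I has 35 patients per arm, Phase II 70.
- Phase I arm, two lost: 4/35 = 11.4% becomes 2/33 = 6.1%.
- Phase II arm, two lost: 7/70 = 10.0% becomes 5/68 = 7.4%.

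The rate behaves the same way. Assume 10 hours of monitoring for each of the two lost patients and 48 hours for the other 33. The FAS rate is 4/(33 × 48 + 2 × 10) = 4/1604 = 0.249 per 100 hours. The PPS rate is 2/1584 = 0.126.

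**Phase comparison.** Suppose a true 20% in both phases, the 3.4% ceiling in Phase I (k = 70 × 0.017 = 1.19) and no loss in Phase II. Phase I becomes (14 − 1.19)/(70 − 1.19) = 18.6% against 20.0%, a spurious 1.4 points.

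**Net direction with all early stoppers.** If 28 of 210 fall outside the PPS and a share q of them met the endpoint, the FAS proportion is (182 × p + 28 × q)/210, where p is the PPS proportion.
- p = 10%: q = 10%, 50%, 100% give FAS 10.0%, 15.3%, 22.0%, so the PPS understates by 0 to 12.0 points.
- p = 50%, q = 10%: FAS 44.7%, so the PPS overstates by 5.3 points.

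**The case against.** The mechanism is permitted, not mandated. Protocol 8.7 says monitoring may be discontinued on discharge from the ward; nowhere do the documents say it must stop at ICU transfer or intubation, and the monitoring form records transfers within the hospital. A reader might infer that every such patient is lost. The text does not support that, and the number is unknown. Deterioration after 24 hours of effective time stays in the PPS.

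A reader might also infer that the primary incidence is biased downward. That holds only if those excluded have a higher endpoint proportion than those kept. The rule also removes patients who stop for intolerance, poor signal or early discharge, and the p = 50% case shows the sign can reverse.

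Nor do the documents support a claim that a real Phase II benefit is hidden or reversed. Losing 4 of 70 in Phase I and 2 of 140 in Phase II, at a true 20%, would give 10/66 = 15.2% against 26/138 = 18.8%. But 4/70 is 5.7%, above the whole 3.4% ceiling, and the example assumes no true benefit.

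Finally, 3.4% is not a ward-onset rate: its definition includes postoperative mechanical ventilation, and ventilated patients are excluded from the study. Even at that ceiling the overall shift of 1.6 points lies inside the planned 5-point precision. ICU transfers, serious events and deaths are still analysed in the FAS, and SAP 7.1.1 already reports FAS and PPS numbers by device, with reasons where known. The study is a pilot with a descriptive primary estimate.

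All of this stands, and it limits the size and direction that can be claimed. It does not answer the conflict with Protocol 12.3 or justify a primary set that can select on outcome. SAP 7.12 does not help either: it allows the 24-hour cut-off to change if it proves unreachable, but makes no provision for deteriorating patients.

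**Conclusion.** The SAP is wrong as written on this point and should be corrected before analysis. It contradicts Protocol 12.3 on the primary set, and its own choice can remove patients who have already met the endpoint. Under the stated assumptions the overall effect is small: 10.0% becomes 9.9% to 8.4%, or 37.0% becomes 35.9% at the ceiling. It can be material in the cells actually reported, where two patients move 11.4% to 6.1%. The actual number lost, the net direction and any difference between phases cannot be determined from the documents. The finding does not establish a downward bias or a masked benefit.

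**What to change.** Reconcile SAP 7.1.3 and 7.9.1 with Protocol 12.3:
- Make the FAS the set for the primary endpoint and secondary endpoint #1. Count every RC marker and all effective monitoring time up to the end of monitoring, whatever its duration. Change the 7.9.1 denominator to FAS person-time.
- Keep the 24-hour PPS as a sensitivity analysis.
- Tabulate PPS exclusions by reason, arm and phase.

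Exempting only deteriorating patients from the 24-hour rule is a less sound repair, because it also selects on outcome. Take 28 short-monitored patients, 3.57 of them deteriorators with the endpoint, no marker in the rest, and a true 21/210 = 10.0%. The exemption gives 21/185.57 = 11.3%; the present rule gives 17.43/182 = 9.6%. If 10% of the rest had a marker, the figures are 10.0% and 8.2%. Which is closer depends on an unknown; the FAS avoids the choice.

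The cost is SAP wording and one derived flag, with no extra patients. Exit reason and care pathway are already collected, and FAS person-time is already needed for secondary endpoint #3. The downside is that the FAS mixes short and long observation, so the plain proportion should be read beside the person-time rate that 7.9.1 already plans.

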## 12.3 Analysis of clinical data

Patient demographics and baseline characteristics will be presented using appropriate summary statistics. This includes mean and standard deviation, minimum, maximum and median with the interquartile range [IQR] for continuous variables and counts and percentages for categorical variables. Summary statistics will be reported with maximum 2 decimals, as appropriate. The SAS software (SAS Institute Inc., Cary, NC, USA) will be used to perform statistical analyses. Statistical tests will be based on a two-sided significance level of 0.05. Graphical representations will be used as deemed appropriate. No adjustments for multiple comparisons or multiple look at data will be performed. Outliers and influential observations will be identified via graphical plots and according to study team decision the analysis could be repeated excluding potential outliers. In case of missing data, no imputation method will be implemented for analysis.

The Full Analysis Set (FAS) will be used for primary final analysis. Any patient who does not satisfying the inclusion/exclusion criteria will be eliminate from the FAS population. Details of endpoints analyses and additional analysis will be described in the Statistical Analysis Plan. The analyses of primary objective on the proportion of patient with at least one RC markers will be reported together with their 95% confidence intervals and separately for each arm and phase of the study (see primary endpoint definition). When comparison of clinical primary outcomes is conducted the propensity score methods could be used to control for biases and confounding which may be due to the nature of this study. The

difference between the two groups within phase and between phases within groups will be analyzed by means of unpaired t-test or Mann-Whitney test according to the normal or non-normal distribution. For one secondary outcome the logistic regression model will be used to check potential predictors. Bivariate odds ratios (ORs) and 95% confidence intervals (95% CIs) will be estimated for each predictor. A multivariate logistic regression model will be performed according to univariate model's results. Other secondary outcomes will be performed using sensitivity and specificity analysis.

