## 7.4. Handling of Missing, Unused, and Spurious Data and Dropouts

Since the impact of missing data is expected to be small, no multiple imputation method for missing data is planned. However, the issue of missing data could arise; the choice of the imputation method for missing data will depend on the pattern of missing data and the type of the imputed variable.

The missing device data will not be imputed and the minimal device data requirement for inclusion is at least 90% of time continuously monitored.

Outliers and influential observations will be identified via graphical plots. Once identified outliers, or influential observations the study team will be informed and according to their decision the analysis for primary endpoint will be repeated excluding the outliers.

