### 7.9.2. Secondary Endpoints

The secondary endpoints are:

1. To compare phases in terms of Primary endpoint incidence;
2. To compare phases in terms of respiratory and SAE incidence, number of ICU transfers and related length of stay, Code blues and RRT responses.
3. To evaluate the rate of clinical early interventions performed by nurse staff to prevent a potential AE, introducing continuous monitoring devices connected to a remote monitoring platform;
4. To evaluate the nurses’ satisfaction related to the monitoring system introducing continuous monitoring devices connected to a remote monitoring platform;
5. To establish the Predictive values of  $\text{EtCO}_2$ , RR,  $\text{SpO}_2$ , plethysmography-derived RR, IPI and EWS in respect to respiratory and other SAE.

In order to evaluate secondary **endpoints #1 and #2**, the incidence of events will be reported together with the comparison between phases, by means of the Chi-square test or Fisher exact test for extreme

proportions, as appropriate. If the monitoring/study exposure results different between phases, also the rates of events will be reported, together with the 95% Poisson Confidence Intervals. The Poisson regression model will be used to calculate the Incidence Rate ratio (IRR), with the d-scale option.

For **endpoint #3**, the rate of clinical early interventions will be calculated as (number of early interventions)/(total time-person in FAS) and it will be reported together with the 95% Poisson Confidence Interval.

Early interventions include, as defined in CRF (Monitoring Period):

1. Stimulated subject to breathe;
2. Repositioned/opened airway;
3. Held or reduced Respiratory Depressive (RD);
4. Added or increased supplemental oxygen;
5. Ventilation support;
6. Other

**Endpoint #4** will be evaluated reporting a summary of the nurses' satisfaction answers.

To identify the predictive values for EtCO2, RR, SpO2, plethysmography-derived RR, IPI and EWS, which can predict respiratory and other SAE, a sensitivity analysis will be performed (**endpoint #5**), and the following parameters will be reported, for each RC marker:

1. **Sensitivity** = 
$$\frac{(\# \text{ of clinical events "Yes" and with RC marker "Yes"})}{(\# \text{ of clinical events "Yes"})} = \frac{TP}{(TP+FN)}$$
2. **PPV** = 
$$\frac{(\# \text{ of clinical events "Yes" and with RC marker "Yes"})}{(\# \text{ of events with RC marker "Yes"})} = \frac{TP}{(TP+FP)}$$

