## **7.12. Changes to Planned Analysis**

If the pre-defined cut-off of 24 hours of monitoring needed for the PPS will be unreachable, future modifications of this cut-off could be considered or, alternatively, a new definition of the populations could be done. Similarly, the 90% cut-off of time continuously monitored could change, accordingly to the study population, as appropriate.

Both the above changes could be applied in order to analyze the higher number of patients from the enrolled ones.

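### The protocol puts the primary analysis in the FAS; the SAP moves it, undeclared, to a PPS needing 24 h of valid signal, gives no FAS estimate and leaves the cut-offs open

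*SAP*

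**What the plan says.** Protocol section 12.3 is explicit: "The Full Analysis Set (FAS) will be used for primary final analysis". The only removals from the FAS that it describes are patients who fail the eligibility criteria; it sets no minimum monitoring time.

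The SAP does something else in three places that agree with each other:

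- The text of section 7.1.3 gives the FAS a role in baseline and safety only, then says "The PPS will be used to describe baseline characteristics of the study population and to evaluate the primary and secondary endpoints".
- The table in section 7.1.3 leaves the FAS cell blank in the column for the primary endpoint and secondary endpoint #1 and ticks the PPS. For secondary endpoints #2 to #5 both sets are ticked.
- Section 7.9.1 defines the denominator of the primary event rate as "total number of time-person in PPS) and will be reported separately for each arm and phase of the study".

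The PPS requires no major protocol deviation and at least 24 hours of effective time, which the SAP footnote defines as cumulative valid recording. For patients with short or poor recordings, or who withdraw, "the analyses will include all data up to the point of their last data collection only for FAS population".

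On the 90% signal rule, section 7.1.3 says that patients below it "will be included or excluded from the PPS, as appropriate", while section 7.4 says "the minimal device data requirement for inclusion is at least 90% of time continuously monitored".

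Section 7.12 allows the 24-hour cut-off, the 90% cut-off and the population definitions to change, and gives the reason: "Both the above changes could be applied in order to analyze the higher number of patients from the enrolled ones". It does not mention the move from FAS to PPS. The SAP version history says only that the SAP was aligned with protocol version 2.0.

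**The concern.** The study exists to quantify how often RC markers occur in high-risk surgical patients on the ward. Its two governing documents name different populations for that number.

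The SAP's population is also defined by what happens after monitoring begins. Adverse event is a listed reason for withdrawal (protocol section 8.12), and monitoring may stop when a patient leaves the ward (section 8.7). A patient who meets an RC marker at hour 6 and leaves monitoring at hour 10 has met the primary endpoint but is counted nowhere in its analysis. Well patients who leave early and patients with poor signal are dropped too, so the net effect could go either way.

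Alarms are silenced in Phase I and active in Phase II. The reasons for falling short of 24 valid hours could therefore differ by phase, and that would carry into secondary endpoint #1, the comparison of phases.

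Finally, because the cut-offs and populations can be altered with no stated time limit, the primary population could be chosen after outcomes are known.

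**Working it through.** **1. The plan's own sample size.** SAP section 6 gives 182 evaluable patients for a precision of 5 percentage points at 10% incidence, with at least 0.80 probability of reaching it, and about 210 enrolled. Taking precision as the half-width of an exact (Clopper-Pearson) 95% interval, the smallest n is 179, and the probability at n = 182 is 0.855. Inflation: 182 × 1.15 = 209.3. The SAP figures reproduce.

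**2. What the choice of set does to that precision (whole cohort).** If the full 10% + 5% allowance is lost, 210 × 0.85 = 178.5, so about 178 remain. The exact-interval probability of reaching 5 points at 10% incidence is then 0.756, against 0.982 if all 210 are analysed. Wald or Wilson intervals give 0.919 at 178. The FAS does not cost precision.

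**3. Shift between PPS and FAS incidence.** Let F be the FAS incidence, r the PPS incidence, e the share of the FAS excluded from the PPS, and k the risk in excluded patients relative to retained patients. Then F = (1 − e)r + e·k·r, so r = F / [(1 − e) + e·k].

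Inputs: F = 10%, the planning minimum in SAP section 6. e = 15% borrows the allowance in the same section (10% dropout plus 5% monitoring-compliance attrition). e = 5% and 30% show the range. k is an assumption; the documents give no figure.

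| e | k = 0.5 | k = 1 | k = 2 | k = 3 |
|---|---|---|---|---|
| 5% | 0.10/0.975 = 10.3% | 10.0% | 0.10/1.05 = 9.5% | 0.10/1.10 = 9.1% |
| 15% | 0.10/0.925 = 10.8% | 10.0% | 0.10/1.15 = 8.7% | 0.10/1.30 = 7.7% |
| 30% | 0.10/0.85 = 11.8% | 10.0% | 0.10/1.30 = 7.7% | 0.10/1.60 = 6.3% |

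**4. Bounds with no assumption about k.** A Phase I arm has 70/2 = 35 patients. Suppose 5 are excluded and the PPS shows 3/30 = 10.0%. If none of the 5 had a marker, the FAS proportion is 3/35 = 8.6%; if all 5 did, it is 8/35 = 22.9%.

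**5. How the two signal rules interact.** Protocol section 8.7 sets a minimum of 24 hours of monitoring, but the PPS needs 24 *valid* hours. A patient monitored for exactly 24 h with 95% valid signal has 24 × 0.95 = 22.8 h and fails, although 95% passes the 90% rule. The SAP does not define the fraction behind the 90% rule; reading it as valid time over recorded time T, the 24-hour rule tolerates a gap of T − 24 and the 90% rule a gap of 0.1T. These are equal at T = 24/0.9 = 26.7 h. Below that the 24-hour rule is the stricter. A 48 h recording with a 3 h gap (45/48 = 93.75%) meets both.

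**6. Is a FAS analysis hidden elsewhere?** The sentence keeping short recordings for the FAS population restores nothing for the primary endpoint, because neither the table in 7.1.3 nor the formula in 7.9.1 uses that set. For endpoint #3 the SAP does use it: "the rate of clinical early interventions will be calculated as (number of early interventions)/(total time-person in FAS". FAS person-time is therefore already to be derived.

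**The case against.** Several points on the other side are fair.

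- **Secondary endpoint #1.** The protocol names no analysis set for it. The defect there is a PPS-only analysis with no FAS counterpart, not a second contradiction. This stands.
- **The 15% is a loose proxy.** Some of the 10% dropout may be patients found ineligible or never monitored, who are outside the FAS as well. In the other direction, the PPS also drops major protocol deviations, which 15% may not cover. This stands, and is why the table gives a range.
- **The shift is small beside the random error.** At 15% excluded it runs from +0.8 to −2.3 points, against a Wald half-width of about 10 points for 35 patients at 10%. The range of 8.6% to 22.9% lies inside the exact 95% interval for 3/30 (2.1% to 26.5%). But a confidence interval does not cover selection bias, so this limits the likely size and does not answer the point.
- **A 24-hour minimum has a rationale.** It matches the protocol's monitoring minimum, and a patient watched for a few hours without a marker is not known to be marker-free. That supports a sensitivity analysis, and the person-time rate already allows for unequal observation. It does not support replacing the protocol's stated set without saying so.
- **The protocol defers detail to the SAP**, requires deviations to be justified in the final report (section 12.2), and the SAP reports FAS and PPS counts by device (section 7.1.1). None of these declares the change or yields a FAS estimate of the primary endpoint.
- **This is a descriptive pilot.** True, but its main product is the incidence estimate, and that is the estimate whose population is in conflict.

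**Conclusion.** The concern holds. For the primary endpoint the protocol and the SAP contradict each other on the analysis set, and the SAP's text, table and formula all take the PPS side without declaring a change. Secondary endpoint #1 is likewise confined to the PPS. The PPS depends on events after the start of monitoring, one of its rules is stated in two incompatible ways, and its cut-offs can be moved. This should be corrected before analysis.

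The size and direction of any bias cannot be known from the documents. With 15% excluded and a risk ratio of 0.5 to 3, both assumptions, a FAS incidence of 10% would be reported as 10.8% to 7.7%. With 5 of 35 patients excluded from a Phase I arm and 3/30 observed, the FAS proportion could lie anywhere from 8.6% to 22.9%. The case rests on the conflict between the documents and the outcome-dependent, movable population; the figures show only what it could amount to.

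**What to change.** 1. In SAP sections 7.1.3 (text and table) and 7.9.1, make the FAS the primary set for the primary endpoint and secondary endpoint #1. Report the proportion with at least one RC marker and its 95% CI by arm and phase, as protocol section 12.3 states, together with the person-time rate using all valid FAS monitoring time.
2. Keep the PPS as a sensitivity analysis, with the 24-hour and 90% cut-offs fixed before outcome data are reviewed and the 90% fraction defined.
3. Make 7.1.3 agree with 7.4 by removing the discretion to include or exclude, and delete the option in 7.12 to change cut-offs or populations. Its stated aim, analysing more of the enrolled patients, is met by the FAS.
4. Report PPS exclusions by arm, phase and reason.

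No time-to-first-event analysis is needed. Section 7.9.1 adjudicates candidate episodes in order of likelihood and stops at the first confirmed one, so the time of the first event is not established.

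The cost is SAP wording and FAS versions of the primary tables. The device data are already collected. Some additional patients may need cross-site adjudication. Short recordings add little information and can pull the simple proportion down; the person-time rate and the PPS sensitivity analysis address that.
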